4. SUBJECT ELIGIBILITY CRITERIA

This study can fulfill its objectives only if appropriate subjects are enrolled. The following eligibility criteria are designed to select subjects for whom participation in the study is considered appropriate. All relevant medical and nonmedical conditions should be taken into consideration when deciding whether a particular subject is suitable for this protocol.

4.1. Inclusion Criteria

Subjects must meet all of the following inclusion criteria to be eligible for enrollment into the study:

1. Is male or female aged at least 3 months at the Screening visit to less than 24 months on Baseline/Day 1.
2. Has a clinical diagnosis of AD according to the criteria of Hanifin and Rajka (1980) (See [Appendix 2](#)).

[REDACTED]

[REDACTED]

- b. [REDACTED]

[REDACTED]

[REDACTED]

[REDACTED]

5. Evidence of a personally signed and dated informed consent document indicating that the subject's parent(s)/legal guardian has been informed of all pertinent aspects of the study.
6. Parent(s)/legal guardian who is/are willing and able to comply with all scheduled visits, treatment plan, laboratory tests and other study procedures.

4.2. Exclusion Criteria

Subjects with any of the following characteristics/conditions will not be included in the study:

1. Has any clinically significant dermatological condition or disease (including active or potentially recurrent non-AD dermatological conditions and/or known genetic dermatological conditions that overlap with AD such as Netherton Syndrome).
2. Was premature at birth, defined as less than 37 gestational weeks.
3. Has estimated creatinine clearance based on the age appropriate calculation that is below the lower limit of normal (LLN), or serum creatinine greater than the upper limit of normal (ULN).
4. Has aspartate aminotransferase (AST) or alanine aminotransferase (ALT) values greater than the ULN.
5. Has received any of the following AD treatment regimens without the required minimum washout:

28 days prior to Baseline/Day 1

- Systemic corticosteroids (use of intranasal/inhaled, and ophthalmic corticosteroids allowed);
- Systemic immunosuppressive agents (eg, methotrexate, ciclosporin, azathioprine, hydroxychloroquine, mycophenolate mofetil).

7 days prior to Baseline/Day 1

- Use of high-or-mid-potency topical corticosteroids or calcineurin inhibitors anywhere on the body;
- Topical antibiotics on treatable AD lesions;
- Light therapy (ultraviolet light therapy);
- Use of antibacterial soaps (for bathing), bleach baths, or topical sodium hypochlorite-based products on treatable AD lesions.

3 days prior to Baseline/Day 1

- Systemic antihistamines;
- Use of low potency topical corticosteroid (eg hydrocortisone 1%) on treatable AD lesions.

8 hours prior to Baseline/Day 1

- Use of emollients on treatable AD lesions;
 - Use of topical antihistamines on treatable AD lesions;
 - Use of topical hydrocortisone <1% on treatable AD lesions.
6. Has unstable AD or a consistent requirement for high-potency topical corticosteroids to manage AD signs and symptoms (see “Prohibited Therapies” for washout periods), or the mother requires treatment with high-potency topical corticosteroids due to potential for topical corticosteroids to transfer to the child.
 7. Child is nursing and the child’s mother requires high dose systemic steroids or systemic immunotherapy or other medications that might be transmitted in the breast milk and that might alter the course of the child’s AD.
 8. Has a history of hyperactive airway disease requiring systemic corticosteroid therapy.
 9. Has a significant active systemic or localized infection, including known actively infected AD, within two weeks prior to Baseline/Day 1.
 10. Has a history of use of biologic therapy including intravenous immunoglobulin (IVIG) at any time prior to study.
 11. Has recent or anticipated concomitant use of topical or systemic therapies that might alter the course of AD, as specified in protocol (see [Concomitant Treatment\(s\)](#)).
 12. Participation in other studies involving investigational drug(s) within 30 days of Baseline/Day 1 and/or during study participation.
 13. Has any planned surgical or medical procedure that would overlap with study participation from Screening through the final study visit on Day 57.
 14. Has undergone treatment for any type of cancer (except squamous cell carcinoma, basal cell carcinoma or carcinoma in situ of the skin, curatively treated with cryosurgery or surgical excision only).
 15. Has a history of angioedema or anaphylaxis to topical products or a known sensitivity to any of the components of crisaborole ointment 2% (listed in [Section 5](#)).
 16. Had previous treatment with crisaborole ointment 2%.

CCI

18. Subjects who have parent(s)/legal guardian who is/are investigator site staff members directly involved in the conduct of the study and their family members, site staff members otherwise supervised by the investigator, or parent(s)/legal guardian who is/are Pfizer employees, including their family members, directly involved in the conduct of the study.
19. Other acute or chronic medical or psychiatric condition or laboratory abnormality that may increase the risk associated with study participation or investigational product administration or may interfere with the interpretation of study results and, in the judgment of the investigator, would make the subject inappropriate for entry into this study.

4.3. Randomization Criteria

This open-label study will enroll subjects sequentially; no randomization will be performed.

4.4. Lifestyle Requirements

- Routine preventative immunizations are permitted during the study; however, it is preferred that immunizations be administered at least 28 days before the start or following the completion of the subject's participation.
- The parent(s)/legal guardian will be instructed to dress the subject in loose-fitting clothing and avoid occluding the treated areas (with dry wraps, for example). Wet wraps are not permitted.
- Subjects should not swim, be bathed or have treatment areas washed for at least 4 hours after application.
- Use of sunscreen is permitted, but only on skin areas without AD involvement.
- If there are treated lesions on the hands or feet, subjects should be encouraged, as much as possible, not to put these areas in the mouth to avoid ingestion of investigational product.
- The parent(s)/legal guardian should avoid wiping the investigational product off the skin and investigational product should not be reapplied to wiped areas until the next scheduled dose.
- If there are AD lesions in the diaper area, they should be treated with investigational product; however, following diaper change, any investigational product inadvertently wiped off soiled skin should not be reapplied until the next scheduled dose. Diaper rash creams, lotions, ointments, powders, etc are not permitted where AD lesions are present. In the case of rash in the diaper area without AD involvement, standard treatments may be applied.

- When applying investigational product at home, the parent(s)/legal guardian will not be required to wear gloves. However, they must be instructed to wash their hands with mild soap and water before and after each application.
- Caregivers who are pregnant, or women of childbearing potential who are trying to become pregnant, should avoid accidental exposure by either avoiding applying investigational product or wearing gloves during its application. Care should also be taken when handling the child after investigational product has been applied.

- CCI [REDACTED]

4.5. Sponsor's Qualified Medical Personnel

The contact information for the sponsor's appropriately qualified medical personnel for the study is documented in the study contact list located in the team SharePoint site.

To facilitate access to appropriately qualified medical personnel on study-related medical questions or problems, subjects are provided with a contact card. The contact card contains, at a minimum, protocol and investigational product identifiers, subject study numbers, contact information for the investigator site, and contact details for a contact center in the event that the investigator site staff cannot be reached to provide advice on a medical question or problem originating from another healthcare professional not involved in the subject's participation in the study. The contact number can also be used by investigator staff if they are seeking advice on medical questions or problems; however, it should be used only in the event that the established communication pathways between the investigator site and the study team are not available. It is therefore intended to augment, but not replace, the established communication pathways between the investigator site and the study team for advice on medical questions or problems that may arise during the study. The contact number is not intended for use by the subject's parent(s)/legal guardian directly, and if a subject's parent(s)/legal guardian calls that number, he or she will be directed back to the investigator site.

5. STUDY TREATMENTS

For the purposes of this study, and per International Conference on Harmonisation (ICH) guidelines, investigational product is defined as a pharmaceutical form of an active ingredient or placebo being tested or used as a reference/comparator in a clinical trial, including a product with a marketing authorization when used or assembled (formulated or packaged) in a way different from the approved form, or when used for an unapproved indication, or when used to gain further information about an approved use (ICH E6 1.33).

For this study, the investigational product is crisaborole ointment 2%. Crisaborole ointment 2% is formulated to contain PF-06930164 (2% wt/wt), white petrolatum, CCI [REDACTED] mono- and diglycerides, paraffin wax, butylated hydroxytoluene, and edetate calcium disodium.

5.1. Allocation to Treatment

The investigator's knowledge of the treatment should not influence the decision to enroll a particular subject or affect the order in which subjects are enrolled.

All subjects will receive crisaborole ointment 2% during their participation in this study. Subjects will be enrolled through the use of an interactive response technology (IRT) system (interactive Web-based response [IWR]). The IRT system will provide a confirmation report containing the subject number and dispensable unit (DU) or container number(s) assigned. The confirmation report must be stored in the site's files.

The study-specific IRT reference manual will provide the contact information and further details on the use of the IRT system.

5.2. Subject Compliance

For subjects in the CC cohort, a subject will be considered compliant with the dosing regimen if they receive at least 12 investigational product doses (no more than 2 missed doses between Day 1 and Day 6) administered in accordance with the protocol. Thereafter, CC cohort subjects will be considered compliant with the dosing regimen if they receive at least 33 but no more than 49 investigational product doses (ie, 80–120%, inclusive, of the expected number of doses) administered in accordance with the protocol.

For Non-PK subjects, a total of 56 doses are expected to be applied. A subject will be considered compliant with the dosing regimen if they receive at least 45 but no more than 67 investigational product doses (ie, 80–120%, inclusive, of the expected number of doses) administered in accordance with the protocol.

Following the Baseline/Day 1 visit, a parent/legal guardian will apply crisaborole ointment 2% to the subject at home for subjects in the nonPK cohort. The CC cohort will have investigational product applied either at the site or at home by a visiting healthcare professional during the PK portion of the study, and the remaining doses applied at home. Compliance with all at-home dosing will be recorded by the parent(s)/legal guardian using a dosing diary provided by the site.

5.3. Investigational Product Supplies

5.3.1. Dosage Form(s) and Packaging

Crisaborole ointment 2% investigational product will be supplied in 60 g tubes. The tubes will be labeled according to local regulatory requirements.

5.4. Investigational Product Storage

The investigator or an approved representative, eg, pharmacist, will ensure that all investigational products are stored in a secured area with controlled access under required storage conditions and in accordance with applicable regulatory requirements.

Investigational products should be stored in their original containers and in accordance with the labels.

Any storage conditions stated in the SRSD will be superseded by the storage conditions stated on the product label.

Site systems must be capable of measuring and documenting (for example, via a log), at a minimum, daily minimum and maximum temperatures for all site storage locations (as applicable, including frozen, refrigerated, and/or room-temperature products). This should be captured from the time of investigational product receipt throughout the study. Even for continuous-monitoring systems, a log or site procedure that ensures active evaluation for excursions should be available. The intent is to ensure that the minimum and maximum temperature is checked each business day to confirm that no excursion occurred since the last evaluation and to provide the site with the capability to store or view the minimum/maximum temperature for all non-working days upon return to normal operations. The operation of the temperature monitoring device and storage unit (for example, refrigerator), as applicable, should be regularly inspected to ensure they are maintained in working order.

Any excursions from the product label storage conditions should be reported to Pfizer upon discovery. The site should actively pursue options for returning the product to the storage conditions described in the labeling, as soon as possible. Deviations from the storage requirements, including any actions taken, must be documented and reported to Pfizer.

Once an excursion is identified, the investigational product must be quarantined and not used until Pfizer provides permission to use the investigational product. It will not be considered a protocol deviation if Pfizer approves the use of the investigational product after the temperature excursion. Use of the investigational product prior to Pfizer approval will be considered a protocol deviation. Specific details regarding information the site should report for each excursion will be provided to the site.

Please see the Investigational Product Manual for additional details on storage conditions and actions to be taken when conditions are outside of the specified range.

Site staff will instruct the subject's parent(s)/legal guardian on the proper storage requirements for take home investigational products. For crisaborole ointment 2%, subject's parent(s)/legal guardian will be instructed to store investigational product at room temperature, away from sunlight or heat.

5.5. Administration

Crisaborole ointment 2% is for external use on the skin only. Large areas that need to be treated can have the ointment applied slowly and segmentally to minimize pain associated with application. Subjects should avoid contact with mucous membranes (ie, inside of nostrils, mouth, vagina, urethra, and rectum), and the eyes. Additionally, for subjects in the [REDACTED] cohort, though AD lesions in the perioral area (within 2 cm of the mouth) or on the extremities (below wrists and below ankles) are exclusionary at baseline, if they occur following enrollment, crisaborole ointment 2% should not be applied to those areas during the [REDACTED] phase (Day 1 AM dose through Day 8 final [REDACTED] sample collection) in order to reduce the possibility of accidental ingestion that could adversely affect [REDACTED] results.

5.6. Preparation and Dispensing of Investigational Product

Within this protocol, preparation refers to the investigator site activities performed to make the investigational product ready for administration or dispensing to the subject/caregiver by qualified staff. Dispensing is defined as the provision of investigational product, concomitant treatments, and accompanying information by qualified staff member(s) to a healthcare provider, subject, or caregiver in accordance with this protocol. Local health authority regulations or investigator site guidelines may use alternative terms for these activities.

The investigational product will be dispensed using an IRT drug management system from Baseline/Day 1 to the Day 15 visit. A qualified staff member will dispense the investigational product via unique container numbers in the cartons provided, in quantities appropriate for the study visit schedule.

For doses to be administered at home, the caregiver (parent(s)/legal guardian) or the visiting health care professional, where applicable, should be instructed to maintain the product in the package provided throughout the course of dosing and return all used and unused product and cartons to the site at the next study visit.

5.7. Investigational Product Application

5.7.1. Non-PK Cohort Subjects

Before the Day 1 initial investigational product application is performed, the designated areas for treatment will be identified at the Baseline/Day 1 visit and documented in the subject's study records. The subject's parent(s)/legal guardian will be provided with a body map documenting the designated treatment areas and a paper dosing diary for recording all investigational product applications applied at home.

Wearing gloves, study staff will apply a thin layer of crisaborole ointment 2% to all treatable AD lesions identified at Baseline/Day 1 for the purpose of instructing the parent(s)/legal guardian how to dispense and apply the ointment. All subsequent doses, including second dose on Day 1, will be applied at home. See [Section 5.8](#) for details regarding study treatment regimen.

The parent(s)/legal guardian will not be expected to wear gloves when applying investigational product at home but will be instructed to wash their hands with mild soap and water before and after each application. The investigational product will be applied to all treatable AD lesions as instructed by study staff.

CCI [REDACTED]

[REDACTED]

[REDACTED]

[REDACTED]

[REDACTED]

[REDACTED]

[REDACTED]

[REDACTED]

[REDACTED]

[REDACTED]

However, if desired, the protocol allows for a visiting health care professional to assist with twice daily doses in the subject's home for some or all of the dose applications during the [CC] portion of the study. This service may be utilized after the Baseline/Day 1 AM dose, based on site and parent(s)/legal guardian agreement. Day 8 AM dosing application and with any 2 of the 3 scheduled [CC] sample collections may also be performed by the visiting health care professional if preferred, however the subject must visit the site for one of the scheduled [CC] sample collections in order to perform the remainder of the Day 8 assessments and procedures.

After the AM dose application on Day 8, the remainder of the doses following the last [CC] sample collection (Day 8 PM dose through the AM dose on the Day 29 visit) will be applied at home by the subject's parent(s)/legal guardian. If preferred, the Day 8 PM dose may be applied at the site. The weighed per application dose is no longer a requirement; rather the parent(s)/legal guardian will be instructed to apply a thin layer of crisaborole ointment 2% BID to all treatable AD-involved areas identified at Baseline/Day 1. Investigational product will continue to be applied to all treatable AD-involved areas (excluding scalp) identified at Baseline/Day 1 regardless of whether they become clinically clear prior to Day 29.

Investigational product may also be applied to any new treatable AD-involved areas that appear following Baseline/Day 1 after consultation with the Investigator at the next scheduled visit. While lesions on the extremities (below wrists and below ankles) or within 2 cm of the mouth are exclusionary at the time of the Baseline/Day 1 visit for subjects in the [CC] cohort visit, new lesions developing in these areas may be treated as appropriate following completion of the Day 8 [CC] sample collections.

For all remaining visits post-Day 8, subjects will arrive at the clinic having had the morning dose applied at home, with the exception of Day 29/Early Termination visit. Dosing should continue up until the PM dose before that visit but no morning dose should be applied on Day 29/ET. The subject's parent(s)/legal guardian will be instructed to apply evening (PM) doses approximately 8–12 hours after the morning (AM) doses (eg, if an AM dose is completed at 8:00 AM, the PM dose can be applied anytime between 4:00 PM and 8:00 PM). In addition, the parent(s)/legal guardian will be provided with a dosing diary to be completed and brought to all study visits after Day 8.

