| Dispense and weigh the investigational product tube(s) and apply first dose. First dose applied in office by study staff | | X | | | | | | |
| Dispense and weigh new investigational product tube(s) and provide for at-home dosing | | X ⁱ | X | X | | | | |
| At-home dosing, applied by parent(s)/legal guardian ^{i,j} | | 2nd dose (PM) on Day 1, then BID up to PM dose prior to Day 29 visit | | | | | | |
| Review dosing diary; assess compliance; re-train parent(s)/legal guardian if doses missed | | | X | X | X | X | | |
| Collect and weigh empty, partially used and unused investigational product tubes | | | X ⁱ | X | | X | | |
| Review and record prior and concomitant medications | X ^k | X | X | X | X | X | X | X |

| Day | | 1 | 8 | 15 | 22 | 29 | 36 | 57 |
|--|------------------|----------------|--------|---------|-------------------|------------------------------------|-------------------|---|
| Window | -28 to -2 day(s) | | ±1 day | ±3 days | ±3 days | ±3 days | ±3 days | +3 days |
| Visit | Screening | Baseline | | | Telephone Contact | End of Treatment/Early Termination | Telephone Contact | Follow-up Contact ^a (End of Study) |
| Assess for AEs (including application site reactions) and SAEs | X | X ¹ | X | X | X | X | X | X |
| Review lifestyle requirements | X | X | X | X | X | X | | |
| Schedule/reconfirm next study visit/contact | X | X | X | X | X | X | X | |
| Remind parent(s)/legal guardian to bring all investigational product tubes (empty, partially used and unused) and the dosing diary to the next visit | | X | X | X | X | | | |

Abbreviations: AD=atopic dermatitis; BP=blood pressure; [REDACTED] PR=pulse rate; RR=respiratory rate; AE=adverse event; SAE=serious adverse event; CCI [REDACTED]; BID=twice a day

- a. Follow-up contact will be completed 28 +3 calendar days after the last administration of the investigational product to capture any adverse events.
- b. Vital signs (temperature, respiratory rate, pulse rate, and BP) taken in seated or supine position after subject has been seated or lying face up for 5 minutes.
- c. A full physical examination will be performed at the Screening visit. If the full examination cannot be completed during screening, an unscheduled visit may be performed prior to Baseline/Day 1 to complete the full assessment.
- d. A limited physical examination will be performed at Baseline/Day 1.
- [REDACTED]
- [REDACTED]

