- g. Blood draw for clinical labs may be completed any time during the screening period, (Day -28 to Day -2) however the results must be available and reviewed by the PI prior to the Baseline/Day 1 visit and investigational product application. If the laboratory sample cannot be obtained due to an upset child, parent or other collections issues, the subject will not be enrolled into the study. Serum chemistry laboratory assessments include lactate and parameters needed to perform calculation of osmolal gap and anion gap.
- [REDACTED] CCI [REDACTED]
- i. Not applicable to subjects in C [REDACTED] cohort through Day 8.
- j. In the event the scheduled Day 29 visit does not fall exactly on Day 29, instruct parent(s)/legal guardian to keep dosing BID until the evening dose prior to the Day 29 visit.
- k. All medications and non-medication therapies used within 30 days prior to Screening.
- l. Assess for AEs (including application site reactions) /SAEs before and after in clinic dose at Baseline/Day 1.

CC Cohort Subjects Only

| Day | 1 ^a | 2-7 | 8 ^b Prior to AM dose (168 hours ±1 hour post time of AM application on Day 1) | 8 3 hours ±20 minutes after completion of AM dose | 8 12 hours ±1 hour after completion of AM dose | Non-PK Study Schedule (see above) ^c |
|---|----------------|-----|---|--|---|--|
| Visit | CCI | | | | | |
| CCI | | | | | | |
| CCI | | | | | | |
| Blood collection for serum chemistry ^{d,f} | | | X | | | |
| CCI | | | | | | |
| Review lifestyle requirements | X | X | X | | | |
| Assess and record any pre- and/or post-dose AEs (including application site reactions) and SAEs | X | X | X | | | |
| Assess and record any changes in concomitant medications | X | X | X | | | |
| Weigh amount of investigational product to be applied before each dose application | X | X | X ^h | | | |
| Dispense dosing diary and train parent(s)/legal guardian on use | | | X | | | |
| Dispense and weigh investigational product tube(s) and provide for at-home dosing | | | X | | | |
| Review the schedule of upcoming study visits with the parent(s)/legal guardian | X | X | X | | | |
| Remind parent(s)/legal guardian to bring all investigational product tubes and the dosing diary to the next visit | | | X | | | |

Abbreviations: CCI

- Perform Day 1 assessments prior to dosing procedures, as applicable (See All Subjects (Including non-C and C Cohorts)).

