- Aside from AM dose application, first C sample collection, serum chemistry CCI sample collection which must all be performed at the first C collection time point, all other Day 8 procedures may be performed at any of the 3 PK collection time points.
- Subject to resume regular study schedule following completion of Day 8/PK 8 final PK sample collection.

█ CCI [Redacted]

█ CCI [Redacted]

f. Serum chemistry laboratory assessments include lactate and parameters needed to perform calculation of osmolal gap and anion gap.

█ CCI [Redacted]

h. Weighing of investigational product on Day 8 applies to the AM dose only.

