- Review the [Lifestyle Requirements](#) with the parent(s)/legal guardian.
- After PI's or designee's documented confirmation of eligibility, access IRT system to receive randomization number.

CCI

- Dispense and weigh investigational product tube(s) before applying first dose; record tube weight(s) in subject's source documents.
- Wearing gloves, study staff will apply a layer of investigational product to all treatable AD lesions identified at Baseline/Day 1.

The following procedures will be performed at the Baseline/Day 1 Visit AFTER dosing with investigational product:

- Assess and record any post-dose AEs, including potential hypersensitivity and/or application site reactions, and SAEs.
- Provide to parent(s)/legal guardian a sufficient number of tubes of investigational product to allow for dosing until the next scheduled visit.
- Instruct the parent(s)/legal guardian regarding investigational product application (see [Section 5.7](#)) to begin with the evening (PM) dose on Day 1 followed by BID dosing up to the PM dose prior to the Day 29 visit.
- Dispense dosing diary and instruct the subject's parent(s)/legal guardian on use (ie, each time study drug is applied).
- Review the schedule of upcoming study visits with parent(s)/legal guardian, and instruct them to return at the scheduled time for the Day 8 Visit.
- Remind the parent(s)/legal guardian to bring all investigational product tubes (empty, partially used and unused) and the dosing diary to their next visit.

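### The PK-cohort regimen text in Protocol Section 5.8 includes a Day 29 morning dose that the same text, and four other places in the protocol, exclude

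*Protocol*

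**What the plan says.** The PK-cohort regimen text stands at the end of Protocol Section 5.8, under a blacked-out heading. Its first visible paragraph on home dosing gives the remaining doses as "Day 8 PM dose through the AM dose on the Day 29 visit) will be applied at home". Its third paragraph says that after Day 8 children arrive "having had the morning dose applied at home, with the exception of Day 29/Early Termination visit", and adds: "Dosing should continue up until the PM dose before that visit but no morning dose should be applied on Day 29/ET".

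Elsewhere in the protocol:

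- **Schedule of Activities, All Subjects, at-home dosing row:** "2nd dose (PM) on Day 1, then BID up to PM dose prior to Day 29 visit". Footnote i exempts the PK cohort from this row only through Day 8.
- **Footnote j to the same table:** if the visit is not exactly on Day 29, families are told to "keep dosing BID until the evening dose prior to the Day 29 visit".
- **Section 6.7 (Day 22 call):** staff tell families not to dose on the morning of the Day 29 visit.
- **Section 6.8 (Day 29 visit):** rules out a home dose that morning, asks for an early-morning appointment, and times the lactate and systemic-level sample at 12 ± 3 h after the Day 28 evening application.
- **Schedule of Activities, PK cohort, footnote:** "Subject to resume regular study schedule following completion of Day 8/PK 8 final PK sample collection".
- **Section 5.2:** after the sampling phase, a PK-cohort child is compliant with 33 to 49 doses, stated as 80–120% of the expected number.

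**The concern.** One parenthetical adds a dose that the rest of the text removes. A site working from that sentence would have the child treated at home on the morning of the visit, then draw the Day 29 blood. The plan intends that sample to sit about half a day after the last application.

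Lactate is a listed safety chemistry test (Section 7.1.1, Table 2). Laboratory parameters are part of the primary endpoint, and SAP Section 6.1.2 summarizes laboratory change from screening at Day 29/Early Termination. The schedule shows no later chemistry draw. A sample taken soon after an application could also pass a window check, because that check is made against the evening dose.

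**Working it through.** **1. Do the other places apply to this cohort?** Footnote i lifts the at-home row for the PK cohort only through Day 8, and the PK-cohort footnote returns these children to the regular schedule after the final Day 8 sample. The at-home row, footnote j, Section 6.7 and Section 6.8 therefore all apply: four places. Section 6.4 has the same end point ("followed by BID dosing up to the PM dose prior to the Day 29 visit"), but its instruction starts with a Day 1 evening home dose given by the parent. In this cohort, site staff or a visiting professional apply the doses at that stage, so Section 6.4 is not counted.

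**2. The plan's own dose counts.** Limits are 0.8N rounded up and 1.2N rounded down.

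- Non-PK subjects, Day 1 AM to Day 28 PM: N = 2 × 28 = 56; 44.8 and 67.2 give 45–67, as Section 5.2 and SAP Section 6.4.3 state. Adding a Day 29 AM dose gives N = 57 and 46–68, which does not match.
- PK cohort after the sampling phase: Section 5.2 gives 33–49 but does not state where this second count starts. The possibilities are:

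| Count starts | Ends Day 28 PM | Ends Day 29 AM |
|---|---|---|
| Day 7 AM | 44 (36–52) | 45 (36–54) |
| Day 8 AM | 42 (34–50) | 43 (35–51) |
| Day 8 PM | **41 (33–49)** | 42 (34–50) |
| Day 9 AM | 40 (32–48) | **41 (33–49)** |

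The range 33–49 fixes N at 41: rounding up to 33 needs 40 < N ≤ 41.25, and rounding down to 49 needs 40.83 ≤ N < 41.67. It does not fix the interval. With a Day 8 PM start, which is where Section 5.8 begins home dosing, the stated range matches an end at Day 28 PM, and the parenthetical would need 34–50. With a Day 9 AM start, it would match an end at Day 29 AM.

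**3. Compliance of a fully dosed child (Day 8 PM start).** For a visit on day V, doses without a visit-day morning dose are 1 + 2(V − 9). V = 26, 29, 32 gives 35, 41, 47; with a morning dose, 36, 42, 48. All lie within 33–49, so the classification does not change.

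**4. Sample timing.** Section 5.8 has families "apply evening (PM) doses approximately 8–12 hours after the morning (AM) doses". If the morning dose keeps its clock time (assumption), the overnight gap is g = 24 − (8 to 12) = 12 to 16 h. The sampling window is 9 to 15 h after the evening dose, so the latest in-window time after a morning dose is 15 − g:

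| Overnight gap g | In-window time after a morning dose |
|---|---|
| 12 h | 0–3 h |
| 14 h | 0–1 h |
| 15 h | 0 h |
| 16 h | none |

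**5. Cohort.** 16/125 = 12.8%; 16 is a minimum (Section 3.1).

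**The case against.** The strongest reply is that this is a one-phrase drafting slip with a thin route to harm. Families act on what the site tells them. The Day 22 call is the last scheduled contact before Day 29, and it addresses the morning dose explicitly. Section 6.8 asks for early-morning scheduling: with doses at 8 AM and 8 PM, a sample 3 h after the morning dose means an 11 AM draw. At the nominal 12 h there is no post-dose interval at all, and after a 4 PM evening dose the window closes at 7 AM, before the next 8 AM dose. All of this stands, and it keeps the point minor. It does not remove the conflict.

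The safeguards are also partial. The Day 8 and Day 15 visits, where home dosing is taught in person, say only that dosing runs through the Day 29 visit (Sections 6.5 and 6.6). Section 6.2 makes out-of-window samples and applications protocol deviations, but its sample type is blacked out and its visible sample times are those of Day 8. Cover of the Day 29 sample cannot be confirmed.

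A reader might infer that the 33–49 range proves no Day 29 morning dose was intended. It does not, because a count from Day 9 AM to Day 29 AM is also 41. Section 5.2 is also unclear about its first period: at least 12 doses with at most 2 missed implies 14 expected, while Days 1 to 6 at two a day hold 12.

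**Conclusion.** The contradiction is real, and the text cannot be followed as written. It rests on two instructions within Section 5.8 and on four other places that apply to this cohort after Day 8. The compliance range supports the same reading only if its second count starts at Day 8 PM, which Section 5.2 does not state; it is supporting evidence, not proof.

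The size is one dose per child. If the parenthetical were followed, an in-window sample could be 0–3 h post-dose with a 12 h overnight gap (assumption); the upper end is unlikely.

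A reader might go on to infer misclassified compliance, a changed analysis population or distorted Day 29 lactate. The documents support none of these. A fully dosed child's status is unchanged on the Day 8 PM start, SAP Section 4.2 defines no per-protocol set, and nothing in the documents gives the size of any effect on lactate or on the redacted analyte. Nor do Sections 6.5 and 6.6 count as further conflicts, since their wording is ambiguous and names no morning dose. Severity: minor.

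**What to change.** Reconcile the two Section 5.8 statements with each other; with the at-home row and footnote j of the Schedule of Activities; with Sections 6.7 and 6.8; and with the dose count behind 33–49 in Section 5.2. One statement should then govern the last dose before the Day 29 visit. State in Section 5.2 the dose at which the second count starts. Check the looser wording in Sections 6.5 and 6.6 in the same edit. Which dosing rule is right is for the sponsor to decide; this review does not propose one.

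The cost is a wording correction in an amendment or clarification letter, with no extra subjects, samples or procedures.
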